6.3. Unscheduled Assessments During Illness

6.3.1. First Illness. If any member of the household, including study participants and other people living in the same household that are not enrolled in the study, develop symptoms consistent with a viral illness, the caregiver will be instructed to fill in a symptom survey. If completion of the symptom survey meets a study-specified threshold in an illness algorithm, the caregiver will be instructed to collect, within 24 hours, unscheduled nasal swabs from all study participants and a stool sample from the affected participant. If the affected household member is not a study participant, she/he will be asked to enroll in the study only for this illness event and to provide a nasal swab and a stool sample. In addition, blood will be collected via a OnDemand device from all study participants that are 2 years old or older three weeks after the first illness event threshold is met. If the affected household member was not a study participant, she/he will also be asked to provide the 3-week blood sample. If the affected household member was not a study participant and refuses to register into the study or provide samples, then this illness event will not be recorded as the first illness event for the household.

6.3.2. Subsequent Illnesses. Subsequent illnesses will only be investigated if the index participant develops symptoms consistent with a viral illness that meet the same study-specific threshold as in the “first illness”. In such case, an extra nasal swab and a stool sample will be collected only from the index participant within 24 hours.

6.4. Sample Collection/Questionnaire Completion Windows

Sample collection and completion of the study questionnaires should take place within the time limits specified in the Schedule of Events (Table A).

Table A. Schedule of Events for All Participants

*The window for sample collection and completion of Symptom and Exposure surveys is (+/-) 4 business days

¹There is no window for the baseline (Week 2) blood collection.

²Additional nasal swab and a stool samples will be collected when a household member shows signs of a viral illness and a study-specified threshold for symptom algorithm has been met. For the first illness, the nasal swab sample will be collected within 24 hours from all study participants, including the affected household member, and a stool sample from just the affected household member. Subsequent illnesses will be assessed only if the index participant is affected; in this case a swab and a stool sample will be obtained within 24 hours only from the index participant.

³A nasal secretion and/or saliva sample may be collected at End of Study.

⁴Nasal swabs will be collected at Week 20, 22, 26 and 28 and Health Check Surveys at Week 19, 21, 23, 25, and 27 from participants that agree to participate in the study extension.

⁵An end of study blood sample will be collected from all study participants that are at least 2 years old at Week 24 or at Week 28, if the participant decided to continue in the study with the original visit plan or agreed to participate in the extension, respectively.

⁶An additional blood sample will be collected from all study participants that are at least 2 years old three weeks after a first illness in the household and a study-specified threshold for the symptom algorithm has been met.

7. Laboratory Assays

- SARS-CoV-2 detection and nasal transcriptomics. RNA extracted from all swabs will be used to perform RT-qPCR for SARS-CoV-2. The remaining RNA and DNA will be stored for possible detection (and quantification) of other respiratory viruses, for generating the host transcriptome response to infection (from airway epithelial and any immune cells that were present on the nasal swab), and for delineating the nasal microbiome at the time the swab was collected.
- Viral Serology (antibody detection/quantification) on stored serum. The optimal assay for detection of virus-specific antibody has not yet been identified in the greater scientific community. Serum samples will be stored until such an assay becomes available.
- SARS-CoV-2 detection in stool. RNA extracted from all stool swabs will be used to perform RT-qPCR for SARS-CoV-2. The remaining RNA will be stored for possible detection (and quantification) of other respiratory viruses.

8. Biospecimen Storage

All biological samples will be collected by the caregiver and mailed to the study biorepository.

9. Criteria for Participant and Study Completion and Premature Study Termination

9.1. Participant Completion

Participation of the index participants, caregiver, and sibling(s) will be complete at Week 24 (original schedule of events) or Week 28 if the household agrees to the study extension.

9.2. Participant Stopping Rules and Withdrawal Criteria

Participants may be prematurely terminated from the study for the following reasons:

- The participant elects to withdraw from all future study activities
- The participant is “lost to follow-up” (i.e., no further follow-up is possible because attempts to reestablish contact with the participant have failed)
- The participant dies
- The Investigator no longer believes participation is in the best interest of the participant
- If the index participant’s enrollment is terminated, the caregivers’ and siblings’ participation will be terminated; however, termination of enrollment of the caregiver or sibling will not result in termination of the index participant

9.3. Participant Replacement

Participants who withdraw or are withdrawn will not be replaced.

9.4. Study Stopping Rules

The study may be prematurely terminated for the following reasons:

- If protocol continuation poses major new risks to participants or study staff
- If, as a result of the COVID-19 pandemic circumstances, protocol feasibility becomes highly questionable

10. Safety Monitoring and Reporting

10.1 Overview

This section defines the types of safety data that will be collected under this protocol and outlines the procedures for appropriately collecting, grading, recording, and reporting those data. Adverse events (AEs) that are classified as serious will be reported promptly to DAIT/NIAID. Appropriate notifications will also be made to the site principal investigators.

10.2 Definitions

10.2.1 Adverse Event

For this surveillance study, an adverse event (AE) is defined as any untoward or unfavorable medical occurrence in a participant that is associated with a study procedure mandated by the protocol and occurs within 48 hours of this procedure. This definition excludes all untoward or unfavorable medical occurrences not related to a study procedure, including hospitalizations or deaths. The study mandated procedures are listed in the Schedule of Events (Table A). Criteria for determining the relatedness of an AE to a study procedure and grading its severity are provided in Sections 10.3.1 *Grading Criteria* and 10.3.2 *Attribution Definitions*. The worsening of a participant's pre-existing medical condition will not be considered an AE unless the worsening is related to a study mandated procedure.

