5.1 Risks of Study Procedures

5.1.1 Nasal Swabs and Nasal Secretions

- a. Nasal swab and nasal secretion collection may cause localized discomfort. Rarely, mild epistaxis may occur.
- b. There is a risk of irritation if the liquid reagent in the nasal swab collection kit comes in contact with the skin. Gloves will be provided to reduce the risk of skin contact.
- c. Risk of infection: It is unknown whether the collection of the biospecimens outlined in this protocol increases the risk of infection to household members beyond that of living in the same household with study participants. There is a distinction between what should be expected in a healthcare setting and the home. In this respect, home collection probably does not merit use of the level of personal protective equipment (PPE) recommended for healthcare workers. Because it is not known whether the collection of the biospecimens outlined in this protocol increases the risk of infection to household members beyond that of living in the same household with study participants, we include viral transmission as a potential risk of study participation. Because we do not know if there is an increased risk of infection transmission, as a precaution, the study will provide, recommend, and teach proper use of barrier protection to those assisting with biospecimen collection (collection of anterior nasal swab in age 10 and under, inferior turbinate swab for age 11+, stool swab, capillary blood collection).

Personal Protective Equipment (PPE) plan: The proposed PPE plan for this study is based on available data and guidance from the CDC at the time the study was implemented to prevent any significant additional infectious risk to the family members performing the swabs given both the nature of the procedure being non-aerosol generating and the ongoing level of contact within the household.

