3. **Ethical use of PPE:** At the time of development of this protocol, PPE shortages, including N95 masks are currently (March – April 2020) posing a tremendous challenge to the US healthcare system because of the COVID-19 pandemic. Healthcare facilities are having difficulty accessing the needed PPE and are having to identify alternate ways to provide patient care. There is an Emergency Use Authorization (EUA) of Respiratory Protective Devices; on February 4, 2020, the HHS Secretary declared that circumstances exist to justify the authorization of emergency use of additional respiratory protective devices in healthcare settings during the COVID-19 outbreak. Thus, recommending PPE for this protocol in excess of what has been included and in the absence of any likely benefit would not be responsible use of limited resources and could not be endorsed.

Summary: In summary, it is unknown whether the collection of the biospecimens outlined in this protocol increases the risk of infection to household members beyond that of living in the same household with study participants. Because of this uncertainty, viral transmission is included as a potential risk of study participation, and a barrier protection plan is recommended. However, the collection of these samples by household members does not merit use of the level of PPE recommended for healthcare workers. Thus, use of a surgical mask, eye shield, gloves, and education on proper use, in addition to hand hygiene, are deemed to provide protection for household members assisting with biospecimen collection. These recommendations were developed based on there being a clear distinction between what should be expected in a healthcare setting and the home, and the procedures being conducted. It is not known whether our recommendation of barrier protection precautions for those living in the same household who assist with biospecimen collection are even necessary, but the benefits seem plausible, and the harms unlikely.

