5.1.2 Blood Collection

The risks associated with drawing blood via the OnDemand device include syncope, local discomfort where the lancet is inserted, and, in rare cases, local infection. Participants are instructed to remain seated while using the OnDemand device and during blood collection and to lay down if a participant feels light-headed or experiences dizziness. Universal precautions will be followed to reduce the risk of infection.

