10.2.2 Serious Adverse Event (SAE)

SAEs are very unlikely to occur and reportable SAEs for this surveillance study will be limited to those related to study procedures. An SAE is defined as an AE meeting 1 of the following conditions:

- Death.
- A life-threatening event: An AE is considered "life-threatening" if, in the view of either the investigator or the DAIT Medical Monitor, its occurrence places the subject at immediate risk of death. It does not include an AE that, had it occurred in a more severe form, might have caused death.
- Inpatient hospitalization or prolongation of existing hospitalization.
- Persistent or significant incapacity or substantial disruption of the ability to conduct normal life functions.
- Important medical events that may not result in death, be life threatening, or require hospitalization may be considered serious when, based upon appropriate medical judgment, they may jeopardize the participant and may require medical or surgical intervention to prevent one of the outcomes listed above.

Any other condition that, in the judgment of the investigator, represents a significant hazard, such as an important medical event that does not result in one of the above outcomes, may be considered an SAE when the event is related to a study procedure and jeopardizes the participant or requires medical or surgical intervention to prevent one of the outcomes listed above.

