10.3.2 Attribution Definitions

For the purpose of this surveillance study, only AEs related to a study-mandated procedure will be reportable and by definition will always be assessed as related. The degree of certainty about relatedness will be graded using the 2 categories below.

Table 12.3.2 Attribution of Adverse Events

Code	Descriptor	Relationship (to study procedure)
RELATED CATEGORIES		
2	Possibly Related	The adverse event has a reasonable possibility to be related; there is evidence to suggest a causal relationship.
3	Related	The adverse event is clearly related.

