10.4.2 Collecting Adverse Events

Adverse events (including SAEs) may be discovered through any of these methods:

- Interviewing the participant through specific questions that will be incorporated in the study questionnaires
- Receiving an unsolicited complaint from the participant

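### The 48-hour limit in the AE definition excludes later-appearing lancet-site infection, a procedure risk that section 5.1.2 itself lists

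*Combined protocol and SAP*

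**What the plan says.** Section 10.2.1 sets two conditions for an AE, and both must be met: the event must be "associated with a study procedure mandated by the protocol and occurs within 48 hours of this procedure".

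Section 5.1.2 gives the risks of the blood-collection device as syncope, "local discomfort where the lancet is inserted, and, in rare cases, local infection". Section 5.1.1 c adds, for sample collection in the home, that "we include viral transmission as a potential risk of study participation". Neither infection risk carries a time limit.

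Section 10.2.2 builds the serious category on the AE definition: "An SAE is defined as an AE meeting 1 of the following conditions". Its last paragraph then says that another hazardous condition "may be considered an SAE when the event is related to a study procedure and jeopardizes the participant" or needs intervention. That paragraph depends on the investigator's judgment and mentions no time window.

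Section 10.3.2 says that "only AEs related to a study-mandated procedure will be reportable" and supplies two grades of relatedness. Section 10.4.2 gives two ways in which AEs are found: unsolicited complaints, and "Interviewing the participant through specific questions that will be incorporated in the study questionnaires". Under 10.6.1 the Medical Monitor receives a monthly compilation of the recorded AEs and SAEs and also judges whether a stopping rule has been met.

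**The concern.** A 48-hour window suits the immediate effects in section 5.1, such as fainting, a minor nosebleed or skin irritation from the reagent. It does not suit infection at a puncture site, which may take longer than two days to show. For that risk the window is an added filter on top of relatedness. An event that the site judges to be caused by the procedure is dropped because of the day on which it appeared.

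What is at stake is the content of the AE and SAE records and of the monthly reports built from them. Blood is taken at home by families. Under the present wording, a run of mild, clearly related, late infections would leave no trace in the only safety reports that the protocol describes. Two sites could also classify the same serious late infection differently, depending on which part of 10.2.2 they follow.

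**Working it through.** There is no calculated figure in the plan to reproduce here. The 48 hours is a definition, so the check is mainly a reading of the sections against each other.

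**Step 1: follow one event through the text.** Take a lancet-site infection first apparent on day 3 that the site considers related.

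- 10.2.1, association with a mandated procedure: met.
- 10.2.1, within 48 hours: not met, since day 3 is past 2 days. The event is not an AE.
- 10.3.2: its relatedness grades apply to AEs. The section does not restate the window, but does not lift it either.
- 10.4.1: collection runs from the first procedure until the participant completes the study, but only for events that already qualify as AEs.
- 10.4.3: follow-up to resolution applies once an AE has been recorded. An infection with signs inside 48 hours is followed; one that starts later is never recorded.
- 10.6.1: the monthly reports contain recorded AEs and SAEs, so a non-serious case is absent.

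**Step 2: the same event, but serious.** By the opening definition in 10.2.2 an SAE is an AE, so the listed criteria (hospitalization, for example) inherit the 48 hours. By the closing paragraph, a related event that endangers the participant or needs intervention may be classed as serious with no time limit. The two parts give different answers, and the second is optional.

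**Step 3: could the study hear of the event?** Section 6.2.2 schedules a health check every 2 weeks from Week 1 and a symptom and exposure survey every 2 weeks from Week 2, so the two alternate weekly. An infection on day 3 after a Week 2 draw would precede the Week 3 health check. If that survey carries the AE questions, the site could learn of the infection and then have to set it aside by definition.

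**Step 4: viral transmission.** Section 5.1.1 c also lists this risk, and 10.2.1 would exclude cases appearing after 48 hours. Unlike lancet-site infection, SARS-CoV-2 infection in participants has a second route: it is the primary outcome (3.2), sought by scheduled swabs and by illness swabs (6.2.1, 6.3). That route does not attribute infection to a procedure.

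**Step 5: size.** The exposure can be bounded. Table A, notes 1, 5 and 6, gives a baseline draw, an end-of-study draw and one more after a first household illness, so 2 to 3 per participant aged 2 or over. Section 3.1 gives 2 to 4 members in each of about 2000 families.

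- 2000 × 2 × 2 = 8,000 draws
- 2000 × 4 × 3 = 24,000 draws

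Both assume full enrollment, everyone aged 2 or over, and no dropout. The upper figure also needs four members and a qualifying illness in every family.

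The share of infections falling outside the window depends on time to onset, which the documents do not give. As an assumption, let onset be lognormal with median m days and log-SD 0.5. Then

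share after 48 hours = 1 − Φ((ln 2 − ln m) / 0.5).

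| Assumed median m (days) | (ln 2 − ln m) / 0.5 | Share after 48 hours |
|---|---|---|
| 1 | 1.386 | 8% |
| 2 | 0 | 50% |
| 3 | −0.811 | 79% |
| 5 | −1.833 | 97% |
| 7 | −2.506 | over 99% |

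The range is almost the whole scale, and the infection rate per draw is also unknown, since 5.1.2 says only that it is rare. No count of missed cases can be supported.

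**The case against.** The strongest reply is that this is a surveillance study that narrows its AE definition on purpose and expects serious events to be very unlikely. A window keeps background illness out of safety reporting during an epidemic. That explains a narrow definition, but 10.2.1 already excludes unrelated events, so for puncture-site infection the window adds little beyond discarding related cases.

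Several stronger readings are tempting, and the documents do not support them.

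- **A late related infection can never be an SAE.** A reader might infer this from the definition of an SAE as an AE. The closing paragraph of 10.2.2 gives serious related events a discretionary route with no time limit. What stands is the inconsistency within 10.2.2.
- **A safety endpoint is biased.** Sections 3.2 to 3.4 define none and section 11 plans no safety analysis. Only AE forms and monthly reports are affected.
- **Infections from sampling go undetected.** For SARS-CoV-2 in participants the study actively looks for them. Section 5.1.1 says it is unknown whether collection adds any risk beyond sharing a household, so single cases could seldom be attributed to a swab. Treating each as possibly related would add noise. Only an explicit statement is lacking.
- **Draws are made by untrained caregivers.** Section 6.1 asks the primary contact and every participant to take web-based training and offers staff support.
- **The Medical Monitor cannot judge the stopping rule.** Section 10.6.1 does not confine that judgment to the AE tables. Mild cases of a risk that 5.1.2 already names would hardly be a major new one.

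It is also fair to say that the questionnaires may already ask about puncture-site infection, because their content is not shown. That does not answer the point: a positive answer about a late infection would still fail the definition.

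**Conclusion.** The point holds in a narrow form. By the plan's own rule, a non-serious lancet-site infection first apparent after 48 hours is not an AE and has no other described route to the Medical Monitor. A serious one is handled inconsistently within 10.2.2. This follows from the wording and needs no numerical assumption, except that an event is taken to occur when it first becomes apparent, which is what a questionnaire can observe.

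The consequence is limited. No study estimate changes, the risk is described as rare, and the number of cases lost is unknown. The correction is still worth making, because the present text takes a risk named in the protocol out of its safety reporting and the remedy is cheap.

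**What to change.** Reconcile 10.2.1 with 5.1.2 and 10.2.2.

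1. In 10.2.1, state that the 48-hour window does not apply to infection at a procedure site. Such an infection, reported at any later study questionnaire or unsolicited, is recorded as an AE if rated possibly related or related under 10.3.2. Keep the window for the other events.
2. In 10.2.2, make the opening definition and the closing paragraph agree on whether an SAE must first meet the AE definition. With the first change, a late procedure-site infection that is serious qualifies under either.
3. Confirm that the AE questions planned in 10.4.2 cover puncture-site infection since the last draw.
4. For viral transmission (5.1.1 c), state that it is assessed through the incidence data and not as an AE.

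The cost is a few sentences, possibly one item in an existing survey, and a few more AE forms. The change does not extend collection past study completion (10.4.1), so it helps less for the final draw, after which few or no questionnaires follow.

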10.2.2 Serious Adverse Event (SAE)

SAEs are very unlikely to occur and reportable SAEs for this surveillance study will be limited to those related to study procedures. An SAE is defined as an AE meeting 1 of the following conditions:

- Death.
- A life-threatening event: An AE is considered "life-threatening" if, in the view of either the investigator or the DAIT Medical Monitor, its occurrence places the subject at immediate risk of death. It does not include an AE that, had it occurred in a more severe form, might have caused death.
- Inpatient hospitalization or prolongation of existing hospitalization.
- Persistent or significant incapacity or substantial disruption of the ability to conduct normal life functions.
- Important medical events that may not result in death, be life threatening, or require hospitalization may be considered serious when, based upon appropriate medical judgment, they may jeopardize the participant and may require medical or surgical intervention to prevent one of the outcomes listed above.

Any other condition that, in the judgment of the investigator, represents a significant hazard, such as an important medical event that does not result in one of the above outcomes, may be considered an SAE when the event is related to a study procedure and jeopardizes the participant or requires medical or surgical intervention to prevent one of the outcomes listed above.

